CONTROL GROUP	
Those in the non-substance-using control condition (MA-/HIV+) will only not receive an intervention. They will only attend four appointments total after their screening to provide blood draws, urine samples, and complete their behavioral surveys.

DURATION OF SUBJECT PARTICIPATION AND DURATION OF STUDY	
Each subject will be on study for up to 17 weeks
 
Screening period: 1-4 weeks
 
Baseline assessment: 1 week
 
Treatment: 8 weeks
 
Follow-up: 4 weeks after end of treatment
 
The total duration of the study is expected to be 4 years. 1 year of rolling subject recruitment, 1 year for final subject follow-up, 1 year of biospecimen processing, and 1 year of analysis.

CONCOMITANT MEDICATIONS	NONE
EFFICACY EVALUATIONS	
PRIMARY ENDPOINT	
 
• A gene expression (mRNA) pattern called the conserved transcriptional response to adversity (CTRA) will be measured using transcriptome profiling of leukocytes.
 

SECONDARY ENDPOINTS	
 
• Negative urine tests for methamphetamine
 
• HIV viral load from plasma
 

OTHER EVALUATIONS	
 
• Plasma concentration of methamphetamine
 
• Short Inventory of Problems Revised (SIP-R)
 
• Sociodemographics – age, race, education level, sexual orientation, housing status, body mass index (BMI), smoking history, and heavy alcohol use history
 

SAFETY EVALUATIONS	
 
• MA use frequency based on urine tests
 
• HIV viral load
 
• Incidence of adverse events
 

PLANNED INTERIM ANALYSES	This will be an NIH-funded study through the K01 mechanism. We have just received requested for Just In Time. When approximately

	50% of patients have completed the study through Week 4, an interim analysis for safety will be conducted when 25% of participants complete Week 4. Serious adverse events will be monitored by the investigators on an ongoing basis throughout the study.
STATISTICS	

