Primary Analysis Plan	Using a linear mixed effects regression, we will test whether a negative MA urine test is associated with reductions in CTRA contrast scores across four time points—Visits B, 4.2 (Week 4), 8.2 (Week 8), and 12.0 (Week 12 follow-up). We will use a time (days) by MA urine result interaction term to estimate difference in change in CTRA as a function of MA test result. Using a mixed effects logistic regression, we will test whether CTRA expression is associated with viral suppression (<200c/mL) across three time points— Visits B, 4.2 (Week 4), 8.2 (Week 8), and 12.0 (Week 12 follow-up). We will include a time (days) by CTRA expression interaction term to test this association longitudinally.
Rationale for Number of Subjects	Power analysis for this pilot study indicates that a minimum of 135 person-observations will be sufficient to test whether MA use or the psychosocial Short Inventory of Problems (SIP-R) are associated with CTRA expression, assuming a medium effect size of 0.15 and power level of .80. Additionally, a logistic model testing whether CTRA is associated with viral suppression would require a minimum of 154 person-observations, assuming a power level of .80, a CTRA standard deviation of 1.44, mean centering of CTRA, and an odds ratio of 1.5. When modeling viral load as a continuous outcome, 135 person-observations is the minimum to test whether CTRA is associated with viral load (c/mL), assuming a medium effect size of 0.15 and power level of .80. These analyses will include 55 participants over four measurements of CTRA, for a total of 220 person-observations (176 person-observations at 80% retention), which is sufficient for these thresholds.

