#### 3.2 Secondary Objectives

- To investigate whether differences in seven psychosocial dimensions of drug addiction (Short Inventory of Problems Revised (SIP-R))—physical, social, intrapersonal, interpersonal, impulse control—are associated with differences in CTRA gene expression.
- To conduct an exploratory pilot investigation to determine the degree to which CTRA mediates the association between MA use and viral suppression.

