### 15.6 Multivariate Analysis for Associations Between Endpoints

Associations between MA use, CTRA gene expression, and viral suppression. All models in Aim 1 will adjust for age, race, education, employment, housing, and mRNA encoding markers of major leukocyte subsets (e.g., CD4). We will also assess for confounding by COVID-19 infection detected by immunoassay, liver function, and type of ART prescription. MA use and CTRA. Using a linear mixed effects regression, we will test whether a negative MA urine test is associated with reductions in CTRA contrast scores across four time points—Visits B, 4.2, 8.2, and 12.0. We will use a time (days) by MA urine result interaction term to estimate difference in change in CTRA as

a function of MA test result. CTRA and viral load. Using a mixed effects logistic regression, we will test whether CTRA gene expression is associated with viral suppression (<200c/mL) across three time points—Visits B, 4.2, 8.2, and 12.0. We will include a time (days) by CTRA gene expression interaction term to test this association longitudinally. We will also test whether CTRA and viral load are reciprocally associated using dynamic panel data modeling with maximum likelihood (102-104). This approach will allow us to simultaneously test whether CTRA is associated with viral load at subsequent observations, and account for whether CTRA is affected by prior values of viral load (102-104).

**Associations between psychosocial indicators of substance use severity and CTRA.** Using a linear mixed effects regression, I will test whether the seven domains of the Addiction Severity Index (ASI) is associated with reductions in CTRA contrast scores across four time points—Visits B, 4.2, 8.2, and 12.0. I will use a time (days) by ASI domain score interaction term to estimate change in CTRA as a function of changes in ASI scoring. We will control for age, race, education, and mRNA markers of major leukocyte subsets.

**Indirect associations between MA use, CTRA, and viral suppression.** I will use propensity scores to test the degree to which CTRA mediates the association between MA use and viral suppression (105, 106). The general theory is that we would compute propensity score for CTRA—the probability of having a particular CTRA level—to compare participants who used MA with those who would have had the same value of the CTRA had they used MA.

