## 15.7 Sample Size and Randomization

This study will enroll 55 participants, who will be evaluated for the course of 14 weeks, including screening. Power analysis for this pilot study indicates that a minimum of 135 person-observations will be sufficient to test whether MA use or the psychosocial Addiction Severity Index (ASI) are associated with CTRA gene expression, assuming a medium effect size of 0.15 and power level of .80. Additionally, a logistic model testing whether CTRA is associated with viral suppression would require a minimum of 154 person-observations, assuming a power level of .80, a CTRA standard deviation of 1.44, mean centering of CTRA, and an odds ratio of 1.5. When modeling viral load as a continuous outcome, 135 person-observations is the minimum to test whether CTRA is associated with viral load (c/mL), assuming a medium effect size of 0.15 and power level of .80. These analyses will include 55 participants over four measurements of CTRA, for a total of 220 person-observations (176 person-observations at 80% retention), which is sufficient for these thresholds.

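### Section 15.6 models the first secondary objective on the ASI although the objective and evaluations name the SIP-R, and the model lists no study-arm term

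*Combined protocol and SAP*

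**What the plan says.** Section 15.6 gives one model for the psychosocial objective, a linear mixed regression of CTRA: "I will test whether the seven domains of the Addiction Severity Index (ASI) is associated with reductions in CTRA contrast scores". It adds a time-by-domain-score "interaction term to estimate change in CTRA as a function of changes in ASI scoring". Its covariates are: "We will control for age, race, education, and mRNA markers of major leukocyte subsets". Study arm is not among them.

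Section 15.7 gives a minimum of 135 person-observations to "test whether MA use or the psychosocial Addiction Severity Index (ASI) are associated with CTRA gene expression". The synopsis gives the same 135, effect size and power to "test whether MA use or the psychosocial Short Inventory of Problems (SIP-R) are associated with CTRA expression". Section 15.7 then states: "These analyses will include 55 participants over four measurements of CTRA".

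Section 3.2, like the synopsis, sets the objective on "seven psychosocial dimensions of drug addiction (Short Inventory of Problems Revised (SIP-R))—physical, social, intrapersonal, interpersonal, impulse control". Section 5.4 and the synopsis list of other evaluations also name the SIP-R. The visit schedules (Table 3 and Appendix 2) show only a behavioral survey and name no instrument.

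Allocation is not randomized (Section 8.1). Controls are excluded for a past or current substance use disorder or for listed substance use in the past 6 months (Section 6.3), and they complete the surveys at the key visits (Section 8.2).

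**The concern.** There are two separate problems.

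First, the ASI appears only in Sections 15.6 and 15.7. No objective, endpoint, evaluation or schedule lists it. An analyst following Section 15.6 would look for domain scores that the rest of the protocol does not say are collected. With seven dimensions announced and five listed, the number of predictors and tests is open too.

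Second, arm is defined by substance use disorder, so a score of substance-use problems should separate the arms almost by construction. The design also allows for CTRA to differ between them: Section 4.1 has controls supply a comparison level, and Section 15.3 compares trajectories by arm. A pooled model without arm can then report an association between score and CTRA when no such relation exists within either group. That would not support the statement in Section 15.6 that CTRA change is estimated as a function of score change.

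**Working it through.** **1. Instrument, place by place**

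| Place | Instrument | Dimensions |
|---|---|---|
| Synopsis objective; 3.2 | SIP-R | says seven, lists five |
| Synopsis other evaluations; 5.4 | SIP-R | none given |
| Synopsis power text | SIP-R | none given |
| 15.6 model | ASI | seven |
| 15.7 power text | ASI | none given |
| Table 3; Appendix 2 | behavioral survey, unnamed | none given |

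**2. The figure of 135.** Inputs from Section 15.7: effect size 0.15, read as Cohen's f², and power 0.80. Alpha and the number of predictors k are not stated; alpha 0.05 is assumed. The method is the noncentral F test for k predictors with noncentrality λ = f² × N.

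- For k = 14 and N = 135: λ = 0.15 × 135 = 20.25 and power is 0.802. The plan's figure is met, but k = 14 was found by working backwards from 135.
- Minimum N is 103 for k = 7, 118 for k = 10 and 139 for k = 15.
- Available: 55 × 4 = 220, and 220 × 0.8 = 176. All these minima lie below 176.

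The count depends on the number of predictors and not on which questionnaire supplies them. It treats repeated observations as independent.

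**3. How an arm gap becomes a score slope.** Suppose there is no relation within arm, a CTRA gap δ(t) at time t, a score gap γ and within-arm score SD 1. The share in the contingency management (CM) arm is p = 35/55 = 0.636, so p(1 − p) = 0.231. At one visit, regressing CTRA on score alone gives the slope δ(t) × γ × 0.231 / (γ² × 0.231 + 1).

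- δ = 0.5, γ = 1: 0.5 × 0.231 / 1.231 = 0.094.
- δ = 0.8, γ = 2: 0.8 × 2 × 0.231 / 1.926 = 0.192.

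If δ is constant, the spurious slope is the same at every visit, and the time-by-score term is not affected. If δ shrinks over time, the slope shrinks with it and shows up in that term.

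**4. Size, by simulation.** Assumed, not in the documents: the gaps below, CTRA ICC 0.5, score ICC 0.6, visit days 0/35/63/91, one score, no other covariates, no missing visits, random-intercept REML, 2,000 replicates. Rejection rate of the time-by-score test without arm, nominal 0.05:

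| CTRA gap, score gap (SD) | Constant gap | Half closed by Week 12 | Fully closed |
|---|---|---|---|
| 0.5, 1 | 0.051 | 0.076 | 0.126 |
| 0.5, 2 | 0.062 | 0.097 | 0.266 |
| 0.8, 1 | 0.051 | 0.101 | 0.286 |
| 0.8, 2 | 0.049 | 0.184 | 0.556 |

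A repeat run gave 6–19% for half closing and 10–51% for full closing. Taking the runs together, the ranges are about 6–19% and 10–56%. If control scores sit at a floor with no variance, half closing gives 8–23% and full closing 17–67%; a constant gap stays at 5–6%. With no CTRA gap, the rate is 5–6%.

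**5. Effect of the arm terms.** With arm and arm-by-time added and the score left unsplit, the time-by-score test rejects in 0.036–0.064 over all these scenarios, with and without the floor.

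**6. Power for a within-person term.** The CM arm supplies 35 × 4 × 0.8 = 112 observations. Removing 35 person means leaves 112 − 35 = 77 within-person degrees of freedom. With λ = 0.15 × 77 = 11.55 and alpha 0.05, power is about 0.71 for five terms and 0.55 for ten.

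**The case against.** **The naming conflict may be no more than leftover wording.** That is plausible, and Section 15 promises a detailed SAP that can modify the plan. But the text is current, this is the only model for the objective, and the choice of instrument should not be left to the analyst.

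**The power statement is unaffected.** This stands. A reader might infer that 135 is wrong because it names the ASI, or that it rests on seven ASI domains because it fits 14 predictors. The documents support neither: Section 15.7 gives no domain count or predictor count, and the synopsis gives the same 135 for the SIP-R.

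**Pooling is inferred.** This also stands. Section 15.6 states no population for this model. Section 15.7 counts all 55 participants for its analyses, which makes pooling the natural reading but not a stated one.

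**A cross-arm association may be what is wanted.** Section 3.2 asks whether *differences* in psychosocial problems go with *differences* in CTRA. For that target an association that runs across arms is real, and adjusting for arm removes part of it. Sections 5.1 and 15.6 speak of *changes*, where it would mislead. The rejection rates above count as false positives only against a target within arm or within person.

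**The inflation is conditional.** A reader might infer that the planned test is badly inflated in general. It is nominal when the CTRA gap is constant. The highest rates need full closure and the largest assumed gaps. Larger figures for the score main effect under a constant gap (11–42%) come from a model without the interaction, which is not the model in Section 15.6.

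**Conclusion.** The instrument conflict and the mismatch between seven and five stand on the text alone. As written, the psychosocial model does not match the instrument named in the objective and evaluations. The SIP-R is the better-supported reading, but the documents do not settle it: Section 5.1 refers to domains of addiction severity, and the schedules name no instrument.

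The missing arm term is a weakness if both arms are pooled. Its effect on the planned time-by-score test runs from none (constant CTRA gap) to about 6–19% (half closing) or 10–56% (full closing), under gaps and correlations that are assumed. A reader might conclude that the score must be split into between-person and within-person parts. The check does not show that, because the arm terms alone remove the inflation. The split follows only from choosing *changes* as the target.

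This should be corrected before the SAP is written. It concerns a secondary objective of a pilot study.

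**What to change.** 1. Make the instrument agree across Section 3.2, the synopsis, 15.6 and 15.7, with the sponsor confirming which it is. Make the dimension count match the list.
2. State whether the target is *differences* or *changes*, and that both arms are analysed.
3. Add arm and arm-by-time to the psychosocial model in Section 15.6. Report any unadjusted pooled association with a label saying that it includes differences between arms.
4. Only if *changes* is kept as the target, also split the score into person-mean and within-person terms, and state in Section 15.7 how many observations inform the within-person term.

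Cost: wording and two model terms, with no new data. In the simulation without a floor, the arm terms raise the score standard error from 0.061–0.07 to about 0.072, and the time-by-score standard error from 0.097–0.123 to about 0.138. The optional split costs more: a within-person standard error of about 0.088, with the power of about 0.71 or 0.55 shown in step 6. If control scores sit at a floor, the score standard errors are 0.070–0.087 without arm, 0.091 with the arm terms and 0.110 with the split.

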**PROTOCOL SYNOPSIS**

TITLE	Expression of stress markers in MSM living with HIV receiving contingency management for methamphetamine use disorder (a.k.a. “EXPRESS+”)
SPONSOR	[name], MPH
FUNDING ORGANIZATION	
NUMBER OF SITES	1
RATIONALE	Determining whether a patient is both feeling better and improving physiologically when treating people living with HIV (PLWH) for methamphetamine use disorder requires identification of a clinically significant measure separate from abstinence. This study will to address this challenge by testing a gene expression (mRNA) pattern identified by the field of social genomics, which may provide insight into both psychosocial health and biological processes that impact chronic disease risk in PLWH receiving MUD treatment.
STUDY DESIGN	This is a within-subjects, two-arm clinical trial with 35 HIV-positive MSM receiving contingency management for treatment of methamphetamine use disorder and 20 HIV-positive MSM serving as a non-substance-using healthy control (N=55 total).
PRIMARY OBJECTIVE	To investigate whether differences in CTRA expression (mRNA) coincide with differences in methamphetamine use and viral load over the course of 12 weeks in HIV-positive MSM with and without methamphetamine use disorder.

SECONDARY OBJECTIVES
	
 
• To investigate whether differences in seven psychosocial dimensions of drug addiction (Short Inventory of Problems Revised (SIP-R))—physical, social, intrapersonal, interpersonal, impulse control—are associated with differences in CTRA gene expression.
 
• To conduct an exploratory pilot investigation to determine the degree to which CTRA mediates the association between METH use and viral suppression.
 

NUMBER OF SUBJECTS
	55

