### Importance of the knowledge to be gained

Information gathered from this study will help to determine whether socially regulated gene expression can serve as a clinically meaningful, non-abstinence-based endpoint for contingency management (CM) for MUD in MSM living with HIV. The potential benefit of this measure as a non-abstinence endpoint to CM for MUD is that it provides information about both psychosocial health and the underlying stress-biology that exacerbates risk of chronic disease. Both of these aspects of health are important to understanding substance use treatment efficacy on a holistic level. Promoting psychosocial health and reducing distress may be important to long-term recovery from MUD, especially for PLWH with MUD. Assessing molecular patterns

linked to MA use and pathogenesis may help in identifying risk and preventing development of MA-related chronic disease. Moreover, identification of a clinical endpoint beyond abstinence may facilitate future approval of therapies for MUD.

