### **5.4 Other Evaluations**

We will assess psychosocial problems with substance use using the Short Inventory of Problems-Revised (SIP-R). Sociodemographics – age, race, education level, sexual orientation, housing status, body mass index (BMI), smoking history, and heavy alcohol use history.

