### 15.2 Demographic and Baseline Characteristics

Sociodemographic and behavioral covariates will include age, race, education level, sexual orientation, employment, income, body mass index (BMI) which is a known risk factor for inflammatory gene expression and a standard biological covariate in social genomics analysis (11, 98-100), smoking history, heavy alcohol use history.

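### No planned model holds MA use and the psychosocial score together, so the plan can show that CTRA is associated with psychosocial problems but not that it informs on them beyond the urine result

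*Combined protocol and SAP*

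**What the plan says.** The psychosocial paragraph of Section 15.6 fits a linear mixed model for CTRA at Visits B, 4.2, 8.2 and 12.0. On the exposure it says "I will use a time (days) by ASI domain score interaction term to estimate change in CTRA", and on adjustment "We will control for age, race, education, and mRNA markers of major leukocyte subsets". Neither MA use nor study group is listed.

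MA use is related to CTRA in a different model of the same section: "We will use a time (days) by MA urine result interaction term to estimate difference in change in CTRA". That model has no psychosocial score. Section 15.3 compares CTRA trajectories between the two groups without the score. The mediation paragraph of 15.6 has viral suppression as its outcome. The general covariate list in 15.2 covers sociodemographics, BMI, smoking and alcohol, but not MA use.

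The synopsis rationale says that the clinical problem "requires identification of a clinically significant measure separate from abstinence". Section 2.1 says the study will help determine "whether socially regulated gene expression can serve as a clinically meaningful, non-abstinence-based endpoint", and gives as the benefit of such a measure that "it provides information about both psychosocial health and the underlying stress-biology that exacerbates risk of chronic disease". Section 1.2 argues in the same direction. The secondary objective in Section 3.2 is narrower: it asks only whether psychosocial differences are associated with CTRA differences.

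**The concern.** Psychosocial problems and CTRA can be correlated simply because both follow MA use. That CTRA moves with MA use is the plan's own primary hypothesis (Section 3.1). A link between the score and MA use is likely on two grounds. Section 5.4 describes the SIP-R as measuring psychosocial problems with substance use. Section 6.3 excludes recent substance users from the control group, so the two groups should differ on both variables.

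If both links hold, the psychosocial model can give a significant score coefficient when CTRA has no relation to psychosocial health other than through drug use. The planned output could not separate that from a genuine psychosocial signal, because MA use and the score never appear in the same model. What is at stake is the use of this result to support CTRA as something more than another marker of MA use.

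**Working it through.** **1. The plan's own figure.** Section 15.7 gives a minimum of 135 person-observations for the MA or psychosocial model, at effect size 0.15 and power 0.80. Alpha and the number of predictors are not stated. I assumed alpha 0.05 and the overall F test of a multiple regression, with f² = 0.15, noncentrality λ = f²·N, and degrees of freedom u and N − u − 1. With u = 14 predictors this gives N = 135 exactly (power 0.802); u = 13 gives 131 and u = 15 gives 139. The 14 predictors are not itemised, so the match does not show whether MA use was counted.

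**2. Size of the induced association.** If CTRA depends on MA use only, then r(score, CTRA) = r(score, MA) × r(MA, CTRA), and f² = r²/(1 − r²). Three of the simulated cases in step 3 give:
- weak: 0.239 × 0.142 = 0.034, f² = 0.001
- middle: 0.432 × 0.234 = 0.101, f² = 0.010
- strong: 0.583 × 0.362 = 0.211, f² = 0.047

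All are well below the planned 0.15. The induced association is small, but 220 rows can still make it significant.

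**3. Rejection rates, no group term.** Simulated design: 35 + 20 participants, four visits, no missing data, random-intercept model, 1000 runs per cell. Assumptions: urine-positive rates of about 85/50/45/55% in the MUD group and none in controls; CTRA SD √(0.6² + 0.8²) = 1.0 apart from the MA effect; true score effect zero. The model holds the score and time, with or without MA. Cells show the percentage of runs in which the score main effect is significant at two-sided 5%, without MA / with MA. Correlations are pooled over both groups.

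| MA effect on CTRA | r(score, MA) ≈ 0.23 | ≈ 0.43 | ≈ 0.58 |
|---|---|---|---|
| 0 | 6.5 / 6.1 | 5.9 / 5.4 | 4.9 / 4.5 |
| 0.3 | 6.6 / 5.2 | 14.0 / 5.0 | 19.4 / 5.1 |
| 0.5 | 11.9 / 5.5 | 27.7 / 6.4 | 45.9 / 4.6 |
| 0.8 | 21.5 / 5.2 | 57.2 / 3.8 | 84.2 / 6.1 |

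The simulation error at a true 5% is √(0.05 × 0.95/1000) = 0.7 percentage points, so the MA-adjusted column is compatible with 5% throughout.

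**4. Effect of a group term.** A separate simulation used MA effects of 0.3 to 0.77 SD and within-group score-MA correlations of about 0.3 to 0.45. Rejection was roughly 7-35% with a group term and 12-66% without one, and about 5% once MA use was added. The upper effect comes from giving the whole f² = 0.15 to MA use: f = √0.15 = 0.387, and for two equal groups 2f ≈ 0.77 SD.

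**5. The interaction term.** Section 15.6 names the time-by-score interaction as its estimator of change. With a constant MA effect of 0.5 to 0.77, correlations of about 0.3 to 0.5 and a group term, the interaction was significant in 4-7% of runs. It rose to 11-29% only when the MA effect on CTRA was made to grow over time.

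**6. Room for the adjustment.** By the method of step 1, adding the MA result needs 139 observations (u = 15), adding MA by time 143 (u = 16), and adding a group term as well 146 (u = 17). All are below the 176 expected at 80% retention, where power is 0.913 for u = 15 and 0.904 for u = 16. Like the plan's figure, these treat repeated visits as independent. Collinearity multiplies the standard error by about 1/√(1 − r²): 1.05 at r = 0.3, 1.12 at 0.45 and 1.15 at 0.5.

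**The case against.** The secondary objective asks for association, and the unadjusted model delivers it. The heading of that paragraph in 15.6 itself calls the scores indicators of substance use severity, so overlap with use is acknowledged. Section 2 describes CTRA as linked to abstinence and as a complement to self-report and urine tests. On that view, being separate from abstinence need not mean being statistically independent of MA use. All of this stands. A reader might infer that the trial fails to answer its own question, or that it will report CTRA as psychosocial information independent of abstinence. The documents support neither: Section 3.2 is answered as worded, and no section commits to such a report.

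Three further limits stand. The inflation falls on the score main effect, while 15.6 names the interaction. An MA effect of 0.77 SD is at the high end, because 135 is reproduced with 0.15 as the joint effect of 14 predictors; a single predictor would need only 55. And the description of the instrument comes from the SIP-R in 5.4, whereas 15.6 names the ASI, whose content the documents do not describe. That the score falls as MA use falls is therefore an inference.

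MA use may also lie on the path between psychosocial problems and CTRA, since Section 1.2 treats such problems as both comorbid with MA use and drivers of CTRA. Adjustment could then remove part of a real effect. This is a reason to report both models, not to leave one out.

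Section 15 promises a detailed SAP, and the study is a pilot. The promise gives an opportunity to add the analysis but does not supply it.

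**Conclusion.** The omission is real and nothing elsewhere in the plan repairs it. As written, the analysis can establish that CTRA and psychosocial scores are associated. It cannot establish that CTRA informs on psychosocial problems beyond the urine result, and a positive finding should not be used for that purpose.

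The size depends on assumptions that the documents do not fix: the MA effect on CTRA, the score-MA correlation and whether a group term is included. The ranges in step 4 are the ones to cite. With a weak MA effect and a weak correlation there is almost no inflation (6.6% in the table); with no MA effect there is none. A reader might infer that the interaction test is invalid too. Under a constant MA effect it is not. The simulations omitted the demographic and leukocyte covariates, so the rates are indicative only.

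**What to change.** In the psychosocial paragraph of 15.6, or in the SAP that Section 15 promises:

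- Fit the model with and without the visit's MA urine result and its interaction with time, and report both sets of psychosocial coefficients.
- State that the unadjusted result shows association only.
- State that any claim that CTRA informs on psychosocial problems beyond MA use rests on the MA-adjusted result, noting that adjustment may remove part of an effect that runs through MA use.

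The cost is a change of wording and one extra model fit. Urine is already tested at all four CTRA visits in both groups (Section 9.2.1 and Table 3). The downside is the modestly wider interval shown in step 6.
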